Exploratory endpoints for exploratory objectives C1 to C6:

- Maternal exploratory endpoint 1: Fold increase in GBS serotype specific IgG antibody titres over baseline measured before vaccination through 12 months after delivery in HIV positive and HIV negative women.
- Maternal exploratory endpoint 2: Serotype specific GBS positive vaginal and/or rectal culture(s) before vaccination, at delivery, and 6 weeks after delivery in HIV positive and HIV negative women

A placebo controlled clinical trial investigating the safety and immunogenicity of GBS6 in pregnant women with and without human immunodeficiency virus (HIV) infection and their infants

Protocol Version 5.0, Dated 01/02/2023

Protocol Version/date 5.0,01/02/2023
R&D Protocol Code Number:
Page:29

- Maternal exploratory endpoint 3: GBS serotype specific IgG and IgA antibody titres in breast milk following vaccination of women living with HIV and their unexposed counterparts in colostrum (within 72 hours of delivery) and breast milk at 6 and 18 weeks after delivery
- Infant exploratory endpoint 1: IgG antibody titres to vaccines included in the extended programme of vaccination administered to HIV-exposed and unexposed infant participants as part of at 18 weeks and 12 months of age.
- Infant exploratory endpoint 2: Serotype specific GBS positive nasal/rectal cultures at delivery, 6 weeks and 18 weeks after delivery in infant participants.
- Infant exploratory endpoint 3 GBS serotype specific IgG antibody titres measured from dried blood spots in infant participants at birth.

A placebo controlled clinical trial investigating the safety and immunogenicity of GBS6 in pregnant women with and without human immunodeficiency virus (HIV) infection and their infants

Protocol Version 5.0, Dated 01/02/2023

Protocol Version/date 5.0,01/02/2023
R&D Protocol Code Number:
Page:30

6. Statistical design

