6.1 Sample size

This is a Phase 2 randomised, placebo controlled, double-blinded study to assess safety, tolerability, and immunogenicity of GBS6 in pregnant HIV positive and HIV negative women and their infant participants. It will be the first evaluation of the investigational GBS6 vaccine in HIV-infected pregnant women. This study will enroll pregnant women with and without HIV to receive the GBS6 in order to provide an expanded safety and immunogenicity data set (for both pregnant women and their infants) and to support progression of the development of this vaccine. As such, the statistical analyses are largely descriptive and the sample size is chosen based on what is achievable at the site. Additionally, and consistent with the clinical phase of the study (II), the primary outcome is based on safety.

Regarding safety, for common pregnancy outcomes such as prematurity, this sample size of 300 in total would provide 80% power (5% alpha) to detect an increase in prematurity outcomes from a background rate of 10% in the placebo arm, to at least 22% in the vaccine arm.

For the secondary objectives of immunogenicity, approximately 300 pregnant women will be enrolled in this study, 150 participants at the selected GBS6 dose/formulation (75 HIV positive and 75 HIV negative) and 150 participants in the placebo group (75 HIV positive and 75 HIV negative). Based on data from a recent study (20), the standard deviation (SD) of the GMT responses to serotypes Ia, Ib and III is expected to be around 2.55 log e units.

With 75 women per group, the study will have at least 80% power (5% alpha) to detect at least 3.24-fold higher antibody responses post-vaccination in vaccinated participants compared with placebo.

A placebo controlled clinical trial investigating the safety and immunogenicity of GBS6 in pregnant women with and without human immunodeficiency virus (HIV) infection and their infants

Protocol Version 5.0, Dated 01/02/2023

Protocol Version/date 5.0,01/02/2023
R&D Protocol Code Number:
Page:31

	HIV-uninfected pregnant women	HIV-infected pregnant women
Placebo	Group 1 (n=75)	Group 3 (n=75)
GBS6 vaccine	Group 2 (n=75)	Group 4 (n=75)

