6.3 Statistical methods

Safety data will be analysed separately for maternal participants and their infant participants.

- Descriptive analysis

A flowchart will be used to summarise the number of mothers approached, consented, recruited, assigned to the different study arms, receiving the intended vaccines, completing the study protocol and analysed for the primary outcome, as recommended by the CONSORT statement (<http://www.consort-statement.org/>).

- Statistical significance and confidence intervals

A placebo controlled clinical trial investigating the safety and immunogenicity of GBS6 in pregnant women with and without human immunodeficiency virus (HIV) infection and their infants

Protocol Version 5.0, Dated 01/02/2023

Protocol Version/date 5.0,01/02/2023
R&D Protocol Code Number:
Page:33

MAKERERE UNIVERSITY
SCHOOL OF MEDICINE
APPROVED AMENDMENT
Valid Until

★ 30 NOV 2023 ★

RESEARCH & ETHICS COMMITTEE
[name]

5% significance will be used and 95% confidence intervals.

- Statistical software

Statistical analyses will be performed on STATA version 15 or similar.

- Missing data

Analysis will be by modified intention to treat (mITT), meaning individuals are analysed according to the group they are randomised to, but only those with at least one blood taken and antibody result will be included, with missing data (e.g. from withdrawals, non-compliers) assumed missing at random. Missing data will be excluded from relevant analyses. The mITT analysis will include blood samples taken outside the recommended timing. A per-protocol analysis will also be performed if there are major protocol deviations. Spurious data will be checked to source records and investigated but included if no cause is identified.

- Outliers, censored data and non-normal data

Outliers will be included in the analyses and investigated assuming no errors have occurred. We will assign all results of <2 a value of 1 for calculation of geometric means. Antibody concentrations will be log-transformed for analyses of mean antibody levels.

- Statistical analysis for each objective and outcome

Statistical Analysis of primary endpoints

The followings are the primary analyses for each of the outcomes related to primary objectives.

- Maternal primary endpoint 1:

Proportion of maternal participants reporting solicited local reactions within 7 days following administration of GBS6 vaccine will be calculated with exact binomial 95% confidence

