Proportions of infants with SAEs, AEs of special interest (major congenital anomalies, developmental delay, and suspected or confirmed GBS infection), and MAEs through 12 months of age and any unsolicited events leading to study withdrawal following administration of GBS6 vaccine will be calculated with exact binomial 95% confidence intervals for each group. Comparison between groups (GBS v Placebo within each HIV strata) will be by Fisher's exact test.

Statistical analysis of secondary endpoints

The followings are the primary analyses for each of the outcomes related to secondary objectives.

- Maternal secondary endpoint 1:

Antibody levels for GBS serotype-specific antibody concentrations measured at baseline, 2 weeks, 1 month after vaccination, at delivery, and 6 weeks after delivery in HIV positive and HIV negative women will be described using box-and-whisker plots with a log-scale y-axis. GMTs of GBS serotype specific antibody concentrations measured at baseline, 2 weeks, 1 month after vaccination, at delivery, and 6 weeks after delivery in HIV positive and HIV negative women will be calculated with 95% confidence intervals post vaccinations and the groups will be compared using unpaired t-tests or the Kruskal Wallis test if log-titres are not normally distributed.

Reverse cumulative distribution curves (RCDCs) of antibody concentrations by vaccine groups will be generated for each GBS6 serotype. Additionally, graphs of geometric means and the associated 95% CIs of the antibody concentrations will be presented at each analysis time point by vaccine group and serotype. The proportions of participants achieving defined GBS6 serotype specific IgG concentrations will be summarised descriptively at prespecified time points as counts and percentages with 2-sided 95% exact CIs by vaccine group and HIV

A placebo controlled clinical trial investigating the safety and immunogenicity of GBS6 in pregnant women with and without human immunodeficiency virus (HIV) infection and their infants

Protocol Version 5.0, Dated 01/02/2023

Protocol Version/date 5.0,01/02/2023
R&D Protocol Code Number:
Page:36

MAKERERE UNIVERSITY
SCHOOL OF MEDICINE
APPROVED AMENDMENT
Valid Until

★ 30 NOV 2023 ★

RESEARCH & ETHICS COMMITTEE
[name]

status. Groups 1 vs 2, 3 v 4 will be compared by a t-test or Kuskal-Wallis test if logged data are not normally distributed.

- Maternal secondary endpoint 2:

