For each serotype, GBS serotype specific IgG GMT measured at baseline, and at delivery in HIV positive and HIV negative women will be calculated for each group with 95% confidence intervals. Groups 1 vs 2, 3 v 4 will be compared using similar methods to those for IgG concentrations.

- Infant secondary endpoint 1:

GMCs of GBS serotype specific IgG concentrations in HIV-exposed and unexposed infant participants measured at birth, 18 weeks and 12 months of life will be calculated at all blood draw visits for each group with 95% confidence intervals. Groups 1 vs 2, 3 v 4 will be compared using similar methods to those for maternal IgG concentrations.

- Infant secondary endpoint 2:

GMTs of GBS serotype specific IgG GMT in HIV-exposed and unexposed infant participants measured at 18 weeks of life will be calculated for each group with 95% confidence intervals. Groups 1 vs 2, 3 v 4 will be compared

- Infant secondary endpoint 3:

For each serotype, placental transfer ratio (infant GMC in cord blood or infant blood collected within 72 h of birth divided by maternal GMC in blood collected at delivery) will be calculated for each group with 95% confidence intervals. Groups 1 vs 2, 3 v 4 will be compared using similar methods to those for IgG concentrations.

Statistical analysis of exploratory endpoints

A placebo controlled clinical trial investigating the safety and immunogenicity of GBS6 in pregnant women with and without human immunodeficiency virus (HIV) infection and their infants

Protocol Version 5.0, Dated 01/02/2023

Protocol Version/date 5.0,01/02/2023
R&D Protocol Code Number:
Page:37

The followings are the primary analyses for each of the outcomes related to exploratory objectives.

- Maternal exploratory endpoint 1: The geometric mean fold ratio with a two-sided 95% CI will be calculated for group 4/group2. To account for differences between HIV positive and negative mothers the ratio of group 4/group 2 will be adjusted in a normal errors regression model on logged titers with terms included for covariates including maternal age, gestation and birth weight.

Maternal exploratory endpoint 2: Proportions of maternal participants with GBS colonisation assessed by vaginal and rectal swab before vaccination, at delivery, and 6 weeks after delivery will be calculated with exact binomial 95% confidence intervals for each group.

Comparison between groups (GBS v Placebo within each HIV strata) will be by Fisher's exact test.

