9.2. Data collection

Data will be collected regarding: previous vaccinations (mother), parity, gravida, illnesses or complications of pregnancy, gestation at birth, birth weight, HIV status (mother and infant), syphilis and hepatitis B and hepatitis C status, CBC, renal and liver function, CD4 count, HIV viral load, medications, maternal age, ethnicity, infant sex and number of siblings. All patient information will be directly inputted into the database using only the unique study identifier.

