11.1.2 Visit 1- Vaccination (Day 1) Visit

- Review laboratory results.
- Ensure that the participant continues to be eligible for the study, meets none of the participants withdrawal criteria as described in Section 11.4, and meets none of the temporary delay criteria as described in Section 8.6.1.
- Prior to vaccination, measure vital signs, including weight, oral temperature, sitting blood pressure and pulse rate, and respiratory rate.

A placebo controlled clinical trial investigating the safety and immunogenicity of GBS6 in pregnant women with and without human immunodeficiency virus (HIV) infection and their infants

Protocol Version 5.0, Dated 01/02/2023

Protocol Version/date 5.0,01/02/2023
R&D Protocol Code Number:
Page:61

- Perform a targeted physical examination, evaluating any clinically significant abnormalities based on history and the participant's self-reported symptoms or complaints since the last visit.
- Perform obstetric examination including but not limited to fundal height, foetal heart tones, and foetal movement.
- Obtain urine sample for glucose and protein testing (urine dipstick).
- Issue the participant a paper diary card and provide instructions on its completion. Ensure that the participant records a baseline assessment of prompted systemic events in the paper diary card prior to vaccination.
- Prior to vaccination, collect a blood sample of approximately 10 mL for immunogenicity assessments and approximately 5 mL for CD4 count and viral load for HIV positive participants.
- Prior to vaccination, obtain one rectal and one vaginal swab for GBS microbiological culture.
- The unblinded dispenser dispenses the investigational product.
- The blinded administrator administers a single 0.5-mL injection of investigational product into the deltoid muscle, preferably of the nondominant arm.
- Blinded site staff must observe the participant for at least 30-minutes after investigational product administration for any acute reactions. Record any acute reactions in the participant's source documents and on the AE page of the CRF, and on an SAE form as applicable.
- Issue a measuring device to measure local reactions and a digital thermometer for recording daily temperatures, and provide instructions on their use.
- Ask the participant to complete the paper diary card from Day 1 to Day 7 (Day 1 is the day of vaccination).

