11.2. Infant participants

11.2.1 Visit 1- Delivery

- Ensure that the participant continues to be eligible for the study and meets none of the participant withdrawal criteria as described in Section 11.4.
- Assign a single participant identifier.
- Record demography (including date of birth, sex, race, and ethnicity) and available birth information, including but not limited to infant participant vital status (live, stillbirth, neonatal death), appearance, pulse, grimace, activity, and respiration (Apgar) score, birth length, birth weight, head circumference, and Ballard score. The complete date of birth (dd-mmm-yyyy) will be collected to critically evaluate the antibody levels and safety profile by age.
- Record available vital signs, including axillary temperature, pulse rate, and respiratory rate.
- Record physical examination evaluating any clinically significant abnormalities within the following available body systems: general appearance; skin; head, eyes, ears, nose, and throat; heart; lungs; abdomen; musculoskeletal; extremities; genitourinary; back; neurological; and lymph nodes.
- Collect a cord blood sample of approximately 10 mL for immunogenicity assessments. If cord blood is unavailable, a blood sample of approximately 2.5 mL may be collected in the infant participants up to 72 hours after delivery.

A placebo controlled clinical trial investigating the safety and immunogenicity of GBS6 in pregnant women with and without human immunodeficiency virus (HIV) infection and their infants

Protocol Version 5.0, Dated 01/02/2023

Protocol Version/date 5.0,01/02/2023
R&D Protocol Code Number:
Page:68

MAKERERE UNIVERSITY
SCHOOL OF MEDICINE
APPROVED AMENDMENT
Valid Until

★ 30 NOV 2023 ★

RESEARCH & ETHICS COMMITTEE
[name]

- Blood spot card collection will be performed using the cord blood sample, or blood draw (up to 72 hours after delivery) if cord blood is unavailable. An additional blood spot card collection will be performed using an infant heel prick up to 72 hours after delivery. A single blood spot card will be collected using blood draw (up to 72 hours after delivery) if cord blood unavailable.
- Obtain nasal and rectal swab samples for GBS microbiological culture.
- Collect and record breastfeeding information.
- Complete the participant's source documents.
- Record AEs as described in Section 13 and 14.
- Record non-study vaccines and all concomitant medications (including herbal remedies and antibiotic medications).

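### Maternal IgG is compared between randomised arms without using the baseline titre already collected, and the HIV comparison adjusts for birth weight but does not name baseline

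*Protocol*

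**What the plan says.** **Randomised contrasts.** Under maternal secondary endpoint 1, Section 6.3 says that "the groups will be compared using unpaired t-tests or the Kruskal Wallis test if log-titres are not normally distributed", and it names the contrasts as Groups 1 vs 2 and 3 vs 4. The paragraph introducing the secondary endpoints calls these the primary analyses. Maternal secondary endpoint 2 takes over similar methods. Confidence intervals are specified for each group's geometric mean; a ratio between arms is not mentioned.

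**Baseline.** Section 11.1.2 instructs sites: "Prior to vaccination, collect a blood sample of approximately 10 mL for immunogenicity assessments". Baseline is also a listed time point of the same endpoint.

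**Power.** Section 6.1 gives at least 80% power at 5% alpha with 75 women per group and an SD of about 2.55 log e units "to detect at least 3.24-fold higher antibody responses post-vaccination in vaccinated participants compared with placebo".

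**HIV contrast.** Maternal exploratory endpoint 1 is defined in Section 5.2 as "Fold increase in GBS serotype specific IgG antibody titres over baseline measured before vaccination through 12 months after delivery". Section 6.3 analyses it as a Group 4/Group 2 ratio, adjusted in a "normal errors regression model on logged titers with terms included for covariates including maternal age, gestation and birth weight". Birth weight is among the delivery records in Section 11.2.1 ("birth length, birth weight, head circumference, and Ballard score"). The only gestation item in the Section 9.2 data list is gestation at birth.

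**The concern.** A pre-vaccination titre that predicts the post-vaccination titre removes variance from the arm comparison at no extra cost. The Protocol measures and describes it, then leaves it out of the test. Its only immunogenicity power statement is a fold difference between arms, yet no between-arm ratio with an interval is planned for the randomised contrasts. If the normality check leads to the rank test, none is available from that test. There are 6 serotypes × 4 post-vaccination times × 2 HIV strata = 48 such contrasts, and the test could differ from one to the next. The one ratio with a stated interval is for the non-randomised Group 4/Group 2 contrast.

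In that contrast the covariates bear on bias as well as precision, because HIV status is not assigned. Birth weight is fixed months after HIV exposure and after vaccination. It cannot confound the 2-week and 1-month titres, and it may itself be affected by HIV. Gestation is not defined. If it means gestation at birth, the same objection applies; gestational age at vaccination, which may range from 27 0/7 to 35 6/7 weeks, is the natural pre-vaccination candidate. Baseline titre is not named, and it is unclear whether the response is the titre or the fold rise.

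**Working it through.** **Inputs.** From Section 6.1: n = 75 per group, SD = 2.55 on the natural-log scale, ratio 3.24 (ln 3.24 = 1.1756), alpha 5%. Two-sided testing is assumed, because it reproduces the stated 80%; one-sided gives about 88%. The correlation ρ between log baseline and log post-vaccination IgG is not in the Protocol; 0.3, 0.5 and 0.7 are assumed.

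**Step 1: the plan's own figure.** The standard error of the log ratio is 2.55 × √(2/75) = 0.416. With a noncentral t on 148 df, power at 3.24-fold is 80.1%, and the ratio detectable with 80% power is 3.236. The stated figure is reproduced: it is an unadjusted two-sample t-test with no allowance for dropout.

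**Step 2: baseline-adjusted comparison.** Residual SD = 2.55 × √(1 − ρ²), 147 df. The equivalent unadjusted size is 75/(1 − ρ²). The 95% CI of the ratio is the estimate multiplied and divided by exp(1.976 × residual SD × √(2/75)).

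| ρ (assumed) | Residual SD | Detectable ratio, 80% power | Power at 3.24-fold | Equivalent n per group | CI factor |
|---|---|---|---|---|---|
| unadjusted | 2.55 | 3.24 | 80.1% | 75 | 2.28 |
| 0.3 | 2.43 | 3.07 | 83.6% | 82 | 2.19 |
| 0.5 | 2.21 | 2.76 | 89.9% | 100 | 2.04 |
| 0.7 | 1.82 | 2.31 | 97.5% | 147 | 1.80 |

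Allowing for chance baseline imbalance (variance × (1 + 1/146)) hardly moves the detectable ratios: 3.08, 2.77 and 2.32.

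**Step 3: less favourable settings.** These are 20,000 simulated trials per setting, ANCOVA with a common slope, true ratio 3.24.

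- *Correlation differs by arm* (vaccine/placebo 0/0.5, 0.1/0.8, 0.3/0.8): power about 82%, 88% and 92%.
- *Many baselines at one floor value*, since Section 6.3 sets every result below 2 to 1: with 50% to 70% of baselines at the floor and an underlying ρ of 0.3 to 0.5, power is about 82% to 87%.

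**Step 4: response scale of the Group 4/Group 2 model.** If the response is log fold rise with no baseline term, and the SD is 2.55 at both times (an assumption), the SD of the change is 2.55 × √(2(1 − ρ)). The detectable ratio is then 4.01, 3.24 and 2.48-fold at ρ = 0.3, 0.5 and 0.7. Below ρ = 0.5, fold rise is less precise than the plain titre.

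Once log baseline is a covariate, the choice no longer matters. If log titre = a + b × group + c × log baseline, then log fold rise = a + b × group + (c − 1) × log baseline, with the same b.

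**The case against.** The strongest reply is that nothing in the randomised comparison is wrong. The t-test is valid, the power figure matches it, and Section 6.1 describes the analyses as largely descriptive with a sample size set by what the site can achieve. The gain rests on a correlation the Protocol does not supply and could be as small as two percentage points of power. Section 6.3 also states generally that "5% significance will be used and 95% confidence intervals", and a t-test on logs yields the ratio and its interval directly, so the missing ratio has full force only for the rank-test fallback.

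For the HIV model, the covariate list is open-ended, and an endpoint defined as fold increase may already bring baseline in through the response. Gestation may well mean gestation at vaccination: eligibility is judged on it, and the screening visit records the last menstrual period, the due date and an ultrasound. The timing argument against birth weight covers only the early titres of an endpoint that runs to 12 months after delivery.

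Most of this stands as a limit on the weight of the point. It does not remove it. Section 6.3 leaves detail to the SAP, but itself fixes the unadjusted tests as primary, so an SAP using ANCOVA would depart from the Protocol. An open list and a loosely worded response leave the reader unable to tell whether baseline is accounted for. At the later time points too, birth weight remains a post-exposure variable that HIV may affect.

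**Conclusion.** The point holds as a recommended change. In the randomised contrasts it concerns precision: at 3.24-fold, power would rise from 80.1% to about 84%, 90% or 98% at assumed correlations of 0.3, 0.5 or 0.7, and stays at about 82% or more in the less favourable settings tried. These figures assume the Protocol's SD of 2.55, complete data on 75 women per group and two-sided 5% testing. The unadjusted test is not biased and the 3.24-fold statement needs no correction.

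In the Group 4/Group 2 model it concerns interpretation. One named covariate certainly arises after vaccination and a second may; baseline is not named; and the response scale is ambiguous. The endpoints concerned are secondary and exploratory.

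**What to change.** In Section 6.3:

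- **Maternal post-vaccination IgG, Groups 1 vs 2 and 3 vs 4:** make the primary analysis an ANCOVA on log IgG with log baseline IgG as covariate, within each HIV stratum. Report the geometric mean ratio with its 95% CI for each serotype and time point. Keep the rank test as a sensitivity analysis, not as a replacement chosen by a normality check.
- **Group 4/Group 2 model:** use log baseline IgG, maternal age and gestational age at vaccination. Drop birth weight or move it to a sensitivity analysis. State the response scale; with log baseline in the model, titre and fold rise give the same group ratio.
- **Missing baseline:** add a rule for women with no baseline result.

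The cost is wording and that one rule. No sample, visit or assay is added, since gestational age at vaccination can be derived from what screening already records. Infant, placental-transfer and breast-milk endpoints have no baseline of their own and stay as written.

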5.2. Primary, secondary and exploratory objectives

A. Primary Objectives

- A1. Primary Objective 1: To describe the safety and tolerability of GBS6 when administered at ≥ 27 0/7 to ≤ 35 6/7 weeks' gestation to pregnant women, with and without HIV, aged ≥ 18 to ≤ 40 years of age and their infants.
- A2. Primary Objective 2: To assess the safety of GBS6 in infants born to HIV positive and negative women who were vaccinated during pregnancy.

B. Secondary Objectives

- B1. Secondary Objective 1: To describe the immunogenicity of GBS6 when administered to pregnant women with and without HIV.
- B2. Secondary Objective 2: To describe GBS-specific antibody levels in infants born to women vaccinated with GBS6 during pregnancy.
- B3. Secondary Objective 3: To assess placental transfer of GBS-specific antibodies from pregnant women vaccinated with GBS6 to their infants.

C. Exploratory objectives

- C1. To describe the persistence of serotype-specific antibody responses to the GBS6 vaccine up to 12 months following delivery.
- C2. Exploratory Objective 2: To characterise GBS colonisation status in maternal participants

A placebo controlled clinical trial investigating the safety and immunogenicity of GBS6 in pregnant women with and without human immunodeficiency virus (HIV) infection and their infants

Protocol Version 5.0, Dated 01/02/2023

Protocol Version/date 5.0,01/02/2023
R&D Protocol Code Number:
Page:27

MAKERERE UNIVERSITY
SCHOOL OF MEDICINE
APPROVED AMENDMENT
Valid Until

★ 30 NOV 2023 ★

RESEARCH & ETHICS COMMITTEE
[name]

- C3. Exploratory Objective 3: To describe the immune responses in breast milk in women with and without HIV vaccinated with GBS6.
- C4. Exploratory Objective 4: To describe the immune responses to Expanded Programme on Immunisation (EPI) administered to HIV-exposed and unexposed infant participants born to maternal participants vaccinated with GBS6.
- C5. Exploratory Objective 5: To characterise GBS colonisation status in infant participants at birth, 6 weeks and 18 weeks of age.
- C6. Exploratory Objective 6: To explore GBS6 antibody levels from dried blood spots in infant participants at birth.

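### The analysis stated for maternal exploratory endpoint 1 is a Group 4/Group 2 ratio only; it does not report the fold rise over baseline to 12 months that the endpoint and objective C1 call for

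*Protocol*

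**What the plan says.** Objective C1 (Protocol 5.2, objectives) reads: "To describe the persistence of serotype-specific antibody responses to the GBS6 vaccine up to 12 months following delivery". The endpoint that serves it (Protocol 5.2, endpoints, maternal exploratory endpoint 1) is "Fold increase in GBS serotype specific IgG antibody titres over baseline measured before vaccination through 12 months after delivery"; it applies to women with HIV as well as to women without.

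Section 6.3 introduces its exploratory analyses with the words "The followings are the primary analyses for each of the outcomes related to exploratory objectives". For this endpoint it then states: "The geometric mean fold ratio with a two-sided 95% CI will be calculated for group 4/group2". To allow for differences between women with and without HIV, that ratio is to be "adjusted in a normal errors regression model on logged titers with terms included for covariates including maternal age, gestation and birth weight". Groups 2 and 4 are the GBS6 recipients without and with HIV.

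The nearest other analysis, maternal secondary endpoint 1 in 6.3, covers IgG "measured at baseline, 2 weeks, 1 month after vaccination, at delivery, and 6 weeks after delivery". The same entry adds that "graphs of geometric means and the associated 95% CIs of the antibody concentrations will be presented at each analysis time point by vaccine group", separately for each serotype.

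Maternal blood for immunogenicity is also drawn 12 months after delivery (sections 9.6 and 11.1.10, Table 1), and section 12.3 has IgG to the six serotypes measured in each blood sample. Section 6.3 closes by leaving detailed analyses, additional exploratory analyses and graphical displays to the SAP.

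**The concern.** The endpoint is a change within each woman, followed over time. The analysis named for it is a contrast between two groups with no visit attached. Persistence is a statement about level: how far above her own starting point a vaccinated woman still is at 12 months. A ratio of one vaccinated group to the other removes that level.

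If 6.3 were followed to the letter, the report could say whether women with HIV differ from women without HIV. It need not say whether either group still has antibody above baseline a year after delivery, which is what C1 asks and what the 12-month maternal serum is suited to show.

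The adjusted model adds a second problem. It is set on logged titres, and baseline titre is not among the named terms. Women are randomised within HIV strata, not between them, so baseline IgG may differ between Groups 2 and 4. A ratio of titres and a ratio of fold rises can then point in different directions.

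**Working it through.** The point disputes no stated figure. The check compares the texts, adds a short illustration, and then asks whether the missing quantity could be estimated usefully.

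**1. Endpoint against analysis**

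| Element | Endpoint (5.2) | Stated analysis (6.3) |
|---|---|---|
| Quantity | fold rise over own baseline | Group 4/Group 2 geometric mean fold ratio |
| Groups reported | women with HIV and women without HIV | one ratio of the two vaccinated groups |
| Time | pre-vaccination through 12 months after delivery | no visit named |
| Baseline titre | built in | not among the named model terms |

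**2. Does another maternal serum IgG analysis in 6.3 fill the gap?**

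- Maternal secondary endpoint 1: last listed time point is 6 weeks after delivery. Its graphs sit under the same entry.
- Maternal secondary endpoint 2: baseline and delivery only.
- Infant secondary endpoint 3 (placental transfer): maternal blood at delivery only.
- Maternal exploratory endpoint 3 goes to 18 weeks, but in breast milk.

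None names maternal serum at 12 months. By contrast, infant secondary endpoint 1 names 12 months and asks for estimates in each group at all blood draw visits.

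**3. What the ratio can and cannot show.** Values are assumed, in arbitrary units. Fold rise = 12-month level / baseline.

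| Case | Baseline G4, G2 | 12 months G4, G2 | Fold rise G4, G2 | Titre ratio G4/G2 | Fold-rise ratio G4/G2 |
|---|---|---|---|---|---|
| A: both persist | 0.10, 0.10 | 2, 2 | 20, 20 | 1.0 | 1.0 |
| B: both wane | 0.10, 0.10 | 0.10, 0.10 | 1, 1 | 1.0 | 1.0 |
| C: unequal baseline, equal fold | 0.05, 0.10 | 1, 2 | 20, 20 | 0.5 | 1.0 |
| D: unequal baseline, equal titre | 0.05, 0.10 | 1, 1 | 20, 10 | 1.0 | 2.0 |

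A and B are opposite answers to C1 and give the same ratio on either reading of the term. C and D show that the two readings disagree once baselines differ.

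**4. Could a group's fold rise be estimated usefully?** Section 6.1 gives 75 women per group and an SD of 2.55 log e units. These are the inputs behind the plan's 3.24-fold detectable difference, which reproduces: ln 3.24 = 1.176 needs 74 per group, and 75 per group gives 80.6% power by the normal approximation or 80.1% by the t-test.

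Assume the same SD at baseline and at follow-up, and a within-woman correlation ρ, which the protocol does not give. The 95% CI for a group's geometric mean fold rise is then the estimate multiplied and divided by

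exp[ t(0.975, 74) × 2.55 × √(2(1−ρ)) / √75 ], with t = 1.993, so that 1.993 × 2.55 / √75 = 0.587.

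- ρ = 0.2: exp(0.587 × √1.6) = 2.10
- ρ = 0.5: exp(0.587 × √1.0) = 1.80
- ρ = 0.7: exp(0.587 × √0.6) = 1.58
- ρ = 0.85: exp(0.587 × √0.3) = 1.38

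These assume all 75 women are sampled; dropout by 12 months would widen them. The calculation shows that the fix is workable. It is not evidence of the mismatch.

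**The case against.** The strongest reply is that 6.3 is a summary. On that view the natural sense of a geometric mean fold ratio, under an endpoint defined as a fold increase, is the fold rise in Group 4 divided by that in Group 2, so each group's fold rise has to be computed on the way. The time points come from the endpoint definition, which reaches 12 months. The covariate list is open-ended and could hold baseline. Summaries by group and visit for an exploratory endpoint are ordinary SAP content, and 6.3 defers detail to the SAP.

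Much of this stands, and it rules out several stronger readings that a reader might infer:

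- *The analysis compares titres only.* This is certain only for the adjusted model. The unadjusted ratio may well be one of fold rises.
- *The 12-month maternal sample has no analysis at all.* The endpoint definition brings it in by implication; what is missing is an analysis that names it and reports it.
- *The whole 12-month visit goes unused.* That visit also closes maternal primary endpoint 4, which has its own analysis.
- *C1 cannot be answered.* Nothing in 6.3 forbids descriptive fold rises.
- *Leaving out the placebo groups is an error.* C1 concerns responses to GBS6, so Groups 2 and 4 are the relevant ones and placebo comparisons are optional.

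What does not stand is that this is only deferred detail. The protocol fixes a primary analysis for this endpoint. On either reading its result is a between-group contrast that equals 1 in both case A and case B. A SAP that elaborated that analysis faithfully would still not report the endpoint.

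**Conclusion.** The point holds, with modest weight. The primary analysis fixed in 6.3 for maternal exploratory endpoint 1 does not report the fold rise over baseline through 12 months. As written it does not describe persistence, and no other maternal serum IgG analysis in 6.3 goes beyond 6 weeks after delivery.

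The reach is one of six exploratory objectives and the 12-month maternal IgG sample, up to 300 women and six serotypes. No primary or secondary conclusion and no power statement depends on it. The conclusion rests on the protocol text alone, since the SAP was not available. The illustrative titres and the correlations in the precision check are assumptions, and the conclusion does not depend on them.

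**What to change.** In 6.3, under maternal exploratory endpoint 1:

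- For each woman, serotype and post-vaccination blood visit, including 12 months after delivery, compute log(IgG at visit / IgG at baseline). Report the geometric mean fold rise with 95% CI by group and visit, at least for Groups 2 and 4.
- Keep the Group 4/Group 2 ratio of fold rises as an additional contrast at named visits, and label it non-randomised. Model either log fold rise, or log titre with log baseline titre as a covariate, and say which. If baselines differ between the groups, a log fold-rise model without baseline and a baseline-adjusted titre model answer somewhat different questions. Once log baseline is a covariate, the group coefficient is the same for both outcomes.
- Optionally, compare Group 2 with Group 1 and Group 4 with Group 3.

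The cost is a few sentences in the protocol, mirrored in the SAP. No new samples, visits or assays are needed.
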